### 6.2.1. Preparation and Dispensing

The IP will be dispensed using an Interactive Response Technology (IRT) drug management system at each visit according to the [SoA](#). A qualified staff member will dispense the IP via unique container numbers in the blister cards provided, in quantities appropriate for the study visit schedule. The participant should be instructed to maintain the product in the blister cards provided throughout the course of dosing and return the blister cards to the site at the next study visit.

### 6.3. Measures to Minimize Bias: Randomization and Blinding

Allocation to treatment will occur via an IRT system. A randomization code using the method of random permuted blocks will be utilized to randomize eligible participants in 1:1:1:1:1:1 ratio (1 to 5 of active dosing regimens of PF-06882961 or placebo) prior to the first dose of IP.

Participants will be stratified at randomization (Day 1) by the presence or absence of metformin as background medication.

The system will be programmed with blind-breaking instructions. Refer to [Section 6.3.2](#) for further details.

#### 6.3.1. Allocation to Investigational Product

Participants will be randomized to receive one of the IP regimens described in Table 3.

**Table 3. Randomized Regimens in Study C3421005**

Regimen	Regimen Description (dosed twice-daily)	Number of PF-06882961 tablets				Number of PF-06882961-matching placebo tablets	
		2.5 mg	10 mg	40 mg	100 mg	2.5 mg	10/40/100 mg
A	Placebo	-	-	-	-	1	3
B	PF-06882961 – 2.5 mg	1	-	-	-	-	3
C	PF-06882961 – 10 mg	-	1	-	-	1	2
D	PF-06882961 – 40 mg	-	-	1	-	1	2
E	PF-06882961 – 80 mg	-	-	2	-	1	1
F	PF-06882961 – 120 mg	-	2	-	1	1	-

Allocation of participants to treatment groups will proceed through the use of an IRT system (interactive Web-based response [IWR]). The IRT system will provide a confirmation report containing the participant number, randomization number, and dispensable unit (DU) or container number assigned. The confirmation report must be stored in the site's files.

IP will be dispensed at the study visits summarized in the [SoA](#).

The study-specific IRT reference manual and IP manual will provide the contact information and further details on the use of the IRT system.

In the event of a Quality Assurance audit, the auditor(s) will be allowed access to unblinded IP records at the site(s) to verify that randomization/dispensing has been done accurately.

### **6.3.2. Breaking the Blind**

The IRT will be programmed with blind-breaking instructions. In case of an emergency, the investigator has the sole responsibility for determining if unblinding of a participant's treatment assignment is warranted. Participant safety must always be the first consideration in making such a determination. If the investigator decides that unblinding is warranted, the investigator should make every effort to contact the sponsor prior to unblinding a participant's treatment assignment unless this could delay further management of the participant. If a participant's treatment assignment is unblinded, the sponsor must be notified within 24 hours after breaking the blind. The date and reason that the blind was broken must be recorded in the source documentation and case report form (CRF).

The study-specific IRT reference manual and IP manual will provide the contact information and further details on the use of the IRT system.

### **6.4. Study Intervention Compliance**

Participant compliance with IP will be assessed at each visit. Compliance will be assessed by counting returned tablets. At V4, which occurs during the first 4 weeks of dosing when participants may be receiving titrated doses as part of their blinded regimen, sites should assess the blister cards for compliance, however the cards should remain in the possession of the participant. Compliance (as assessed by tablet count) will be defined as self-administration, by the participants, of:

- $\geq 89\%$  of the study-supplied placebo administered during the placebo run-in period. Based on the visit window, for a placebo run-in that is 11-13 days, up to 2 missed doses are allowed, and for a placebo run-in that is 14-17 days, up to 3 missed doses are allowed. Participants who do not meet this compliance threshold are not eligible to be randomized into the study (See [Section 5.2](#)).
- $\geq 80\%$  of the study supplied IP from Day 1 through Week 16, inclusive. Investigators must closely follow non-compliant, randomized, participants in order to enhance their adherence to treatment. Any participant who fails to meet the criterion of  $\geq 80\%$  compliance will be re-educated by the site staff on the importance of compliance with IP.

### **6.5. Concomitant Therapy**

Participants in this study will be allowed to be on certain concomitant medications that have been prescribed. Attempts should be made not to alter the doses and regimens of the background medications after randomization and for the duration of participation in this study, except in circumstances where a change in dose is deemed medically necessary. Any changes must be captured in the CRF. Additionally, many over-the-counter medications are also permitted during this study.

Treatments taken within 28 days before the first dose of IP will be documented as prior treatment. Treatments taken after the first dose of IP will be documented as concomitant treatment.

All concomitant treatments, both prescription and over-the-counter taken during the study must be recorded with indication, daily dose, and start and stop dates of administration. All participants will be questioned about concomitant treatment at each clinic visit.

See [Appendix 8](#) for details regarding prohibited concomitant medications. Sites are encouraged to contact the sponsor should there be questions as to whether a medication is permitted or prohibited.

### **6.5.1. Metformin**

At least 80% of all participants are required to be taking metformin monotherapy prior to inclusion in this study as listed in [Section 5.1](#). For participants taking metformin, this study requires that participants have been taking stable doses of metformin for at least 60 days prior to the screening visit. Participants will continue taking their own metformin medication at the same total daily dose that was prescribed prior to study entry through the first follow up visit (ie, Visit 10, Week 17-18), except in circumstances where a change in dose is deemed medically necessary. For study visit days, participants should be instructed to refrain from morning dosing at home and to bring the metformin to the site for dosing at the same time as their blinded IP. For participants taking metformin more than once a day, the timing should be approximately the same on each day.

### **6.5.2. Medications for Glycemic Control**

Aside from metformin, the use of other medications for glycemic control is not permitted in this study unless the participant meets the protocol defined glycemic rescue criteria (see [Section 8.2.5.3](#)).

### **6.5.3. Antihypertensive Medications**

The use of background antihypertensive agent(s) is permitted unless otherwise noted in [Appendix 8](#). Doses of antihypertensive agent(s) must be stable for at least 4 weeks prior to screening and throughout the study, except in circumstances where a change in dose is deemed medically necessary. Any changes in doses of these medications must be captured in the CRF.

### **6.5.4. Lipid Modifying Medications**

The use of background lipid modifying agents is permitted unless otherwise noted in [Appendix 8](#). Doses of such lipid modifying agents must be stable for at least 4 weeks prior to screening and throughout the study, except in circumstances where a change in dose is deemed medically necessary. Any changes in doses of these medications must be captured in the CRF.

### **6.5.5. Glycemic Rescue Medicine**

Participants with hyperglycemia as defined in [Section 8.2.5.3](#) should be offered glycemic rescue medication as an add on to their randomized treatment.

Glycemic rescue medication should be prescribed according to local label and obtained locally. The following glycemic rescue medications may be used: metformin (for those participants who were not taking metformin at randomization), sulfonylureas, or sodium glucose co-transporter 2 (SGLT2) inhibitors. For participants who were taking a submaximal dose of metformin, increasing the metformin dose may be instituted as glycemic rescue medication, as long as the dose does not exceed the highest approved dose in the country of participation.

The following medication are *not* permitted as glycemic rescue medications: GLP-1R agonists, DPP-4 inhibitors, amylin analogues, thiazolidinediones (TZDs) or insulin.

The date of glycemic rescue medication administration as well as the name and dosage regimen of the glycemic rescue medication must be recorded on the CRF.

Participants receiving glycemic rescue medication should continue to follow all protocol specified visits and procedures according to the [SoA](#).

There is no rescue therapy to reverse the AEs observed with PF-06882961; standard medical supportive care must be provided to manage the AEs. Standard medical supportive care must be provided to manage the AEs, including administration of carbohydrates to treat hypoglycemic adverse events (HAE) (see [Section 8.2.5.2.1](#)).

## **6.6. Dose Modification**

### **6.6.1. Considerations for Pausing or Stopping Active Dose(s) Based on Observed Safety**

The decision to stop dosing for 1 or more active dose(s) of PF-06882961 may be considered based on recommendations from the IRC according to their review of unblinded, study-level emerging, observed safety data (see [Section 9.5](#)), for reasons such as the following:

- More than 50% of participants develop a moderate or severe AE in the gastrointestinal system organ class (SOC) not responsive to symptomatic management.

## **6.7. Intervention After the End of the Study**

No intervention will be provided to study participants at the end of the study.

## **7. DISCONTINUATION OF STUDY INTERVENTION AND PARTICIPANT DISCONTINUATION/WITHDRAWAL**

### **7.1. Discontinuation of Study Intervention**

It may be necessary for a participant to permanently discontinue IP. If a safety or tolerability concern arises, in particular if not responsive to symptomatic management, dosing with double-blinded IP may be stopped in an individual participant at investigator discretion.

Per the study estimands, if IP is permanently discontinued, the participant will remain in the study and continue to follow all protocol specified visits and procedures according to the SoA with the exception of dosing activities CCI

The site should notify the Sponsor Medical Monitor or Sponsor Clinician if the below criteria for permanent discontinuation are met.

Note that discontinuation of IP does not represent withdrawal from the study.

See the SoA for data to be collected at the time of intervention discontinuation and follow-up and for any further evaluations that need to be completed.

#### **7.1.1. Criteria for Discontinuation**

Discontinuation of IP must occur for a participant meeting any of the following conditions:

- Criteria for a potential Hy's law case are met (see [Appendix 6](#)).
- Intent to become pregnant or pregnancy confirmed by serum beta human chorionic gonadotropin ( $\beta$ -hCG) testing.

### **7.2. Participant Discontinuation/Withdrawal From the Study**

A participant may withdraw from the study at any time at his/her own request, or may be withdrawn at any time at the discretion of the investigator for safety, behavioral, compliance, or administrative reasons.

At the time of discontinuing from the study, if possible, an early termination visit should be conducted. See the SoA for assessments to be collected at the time of study discontinuation and follow-up and for any further evaluations that need to be completed.

The early termination visit applies only to participants who are randomized and then are prematurely withdrawn from the study. Participants should be questioned regarding their reason for withdrawal. The participant will be permanently discontinued both from the study intervention and from the study at that time.

If a participant withdraws from the study, he/she may request destruction of any remaining samples, but data already generated from the samples will continue to be available, and may be used to protect the integrity of existing analyses. The investigator must document any such requests in the site study records.

If the participant withdraws from the study and also withdraws consent (see below) for disclosure of future information, no further evaluations should be performed and no additional data should be collected. The sponsor may retain and continue to use any data collected before such withdrawal of consent.

When a participant withdraws from the study because of an SAE, the SAE must be recorded on the CRF and reported on the Clinical Trial (CT) SAE Report.

Lack of completion of all or any of the withdrawal/early termination procedures will not be viewed as protocol deviations so long as the participant's safety was preserved.

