### **5.3.4. Contraception**

The investigator or his or her designee, in consultation with the participant, will confirm that female participants have selected an appropriate method of contraception from the permitted list of contraception methods (see [Appendix 4, Section 10.4.4](#)) and will confirm that the participant has been instructed in its consistent and correct use. At time points indicated in the [SoA](#) the investigator or designee will inform the participant of the need to use highly effective contraception consistently and correctly and document the conversation and the participant's affirmation in the participant's chart (participants need to affirm their consistent and correct use of at least 1 of the selected methods of contraception). In addition, the investigator or designee will instruct the participant to call immediately if the selected contraception method is discontinued or if pregnancy is known or suspected in the participant or partner.

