### **8.3.1. Time Period and Frequency for Collecting AE and SAE Information**

The time period for actively eliciting and collecting AEs and SAEs (“active collection period”) for each participant begins from the time the participant provides informed consent, which is obtained before the participant’s participation in the study (ie, before undergoing any study-related procedure and/or receiving IP), through and including a minimum of 28 calendar days, except as indicated below, after the last administration of the IP.

For participants who are screen failures, the active collection period ends when screen failure status is determined.

Follow-up by the investigator continues throughout and after the active collection period and until the event or its sequelae resolve or stabilize at a level acceptable to the investigator, and Pfizer concurs with that assessment.

Investigators are not obligated to actively seek AEs or SAEs after conclusion of the study participation. However, if the investigator learns of any SAE, including a death, at any time after a participant has been discharged from the study, and he/she considers the event to be reasonably related to the study intervention or study participation, the investigator must promptly notify the sponsor.

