### **8.3.3. Follow-up of AEs and SAEs**

After the initial AE/SAE report, the investigator is required to proactively follow each participant at subsequent visits/contacts. For each event, the investigator must pursue and obtain adequate information until resolution, stabilization, the event is otherwise explained, or the participant is lost to follow-up (as defined in [Section 7.3](#)).

In general, follow-up information will include a description of the event in sufficient detail to allow for a complete medical assessment of the case and independent determination of possible causality. Any information relevant to the event, such as concomitant medications and illnesses, must be provided. In the case of a participant death, a summary of available autopsy findings must be submitted as soon as possible to Pfizer Safety.

Further information on follow-up procedures is given in [Appendix 3](#).

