#### **8.3.5.1. Exposure During Pregnancy**

Details of all pregnancies in female participants will be collected after the start of study intervention and until 28 calendar days after the last administration of IP.

If a pregnancy is reported, the investigator should inform the sponsor within 24 hours of learning of the pregnancy and should follow the procedures outlined in [Appendix 4](#).

Abnormal pregnancy outcomes (eg, spontaneous abortion, fetal death, stillbirth, congenital anomalies, ectopic pregnancy) are considered SAEs.

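### No contact is scheduled after the early termination visit, so someone who leaves within 28 days of the last dose can miss the protocol's own 28-day AE/SAE and pregnancy collection

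*Protocol*

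**What the plan says.** **What ends at study exit.** Protocol 7.2 asks for an ET visit where possible when a randomized participant leaves the study, and then states: "The participant will be permanently discontinued both from the study intervention and from the study at that time". For follow-up it refers to the SoA. The participant need not have asked to leave: he or she "may be withdrawn at any time at the discretion of the investigator for safety, behavioral, compliance, or administrative reasons". Collection is stopped outright only where a second step is taken: "If the participant withdraws from the study and also withdraws consent (see below) for disclosure of future information, no further evaluations should be performed".

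**What is required after the last dose.** Section 8.3.1 has AEs and SAEs actively elicited for each participant from consent "through and including a minimum of 28 calendar days, except as indicated below, after the last administration of the IP". Section 8.3.5.1 has pregnancies collected "until 28 calendar days after the last administration of IP", with no exception. Later in 8.3.1 comes: "Investigators are not obligated to actively seek AEs or SAEs after conclusion of the study participation".

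**What is scheduled.** The ET column of the SoA (1.3) includes the AE inquiry, laboratory tests and pregnancy tests. Nothing follows it. V10 and V11 sit at Days 119-126 and 140-147, counted from Day 1 and not from the last dose or the ET visit. V11 may be a phone call.

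**Who stays in.** Under 7.1 and the Withdrawal of Consent text, participants who only stop the investigational product (IP) remain on the SoA.

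**The concern.** The 28-day rule and the visit schedule do not meet for one group: people who leave the study, or are withdrawn by the investigator, fewer than 28 days after the last dose and have not refused contact. A site that follows 7.2 and the SoA to the letter closes these participants at ET. The period in which the protocol itself wants AEs and pregnancies collected can then pass with no planned inquiry.

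The loss is to participant safety and to completeness of the safety data. The main treatment-emergent AE summary uses a 365-day lag (SAP 3.5.1), so it takes in whatever post-dose events were collected, and these participants contribute less to it. The subset summary, which stops two days after the last dose (SAP 3.5.1.1), is largely unaffected. Nothing in the documents points to an effect on the HbA1c endpoint or to a difference between doses.

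**Working it through.** **Inputs**
- Required period: at least 28 days after the last dose (Protocol 8.3.1; 8.3.5.1 for pregnancies).
- V9: Day 112 ± 3, so Days 109-115. V10: Days 119-126. V11: Days 140-147 (SoA).
- Contacts tied to ET or to the last dose: none (SoA).
- Assumption: a participant who completes treatment takes the last dose on the day of V9.

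**The plan's own figure.** Section 4.5 puts V11 about 28 to 35 days after the last dose. From the nominal Day 112: 140 − 112 = 28 and 147 − 112 = 35. This reproduces, so a participant who keeps to the nominal schedule is covered.

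**Early leavers.** If exit is g days after the last dose and nothing is scheduled later, the shortfall is max(0, 28 − g).

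| Days from last dose to exit (g) | Days without scheduled collection |
|---|---|
| 0 | 28 |
| 7 | 21 |
| 14 | 14 |
| 21 | 7 |
| 27 | 1 |
| 28 or more | 0 |

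A participant whose last dose was on Day 30 and who leaves on Day 90 has g = 60 and is not affected.

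**Leaving formally at V10 after finishing treatment at V9.** Scheduled post-dose collection runs from 119 − 115 = 4 days to 126 − 109 = 17 days. The shortfall is 28 − 4 = 24 down to 28 − 17 = 11 days.

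**How many people.** This cannot be derived. The 6 of 98 discontinuations in C3421002 (2.2.2.1) include people who left during follow-up. The 25% drop-out in 9.2 is a conservative allowance for sample size. Neither counts those who leave within 28 days of the last dose and still accept contact.

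**Minor point on V11.** There are 7 × 8 = 56 permitted pairs of V9 and V11 days. For V9 on Days 109 to 115, the V11 days that give at least 28 days number 8, 8, 8, 8, 7, 6 and 5, a total of 50. The other 1 + 2 + 3 = 6 pairs fall 1 to 3 days short; the worst is 140 − 115 = 25 days. A compliant V11 day exists for every V9 day. This is a count of pairs and not a probability.

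**The case against.** The strongest reply is that the duty is already written. Section 8.3.1 applies to each participant, and the one exception it expressly ties to the end of the collection period is screen failure. The SoA calls itself an overview and sends sites to the assessment sections. A site that phones at 28 days is complying, so on this view only a scheduling reminder is missing. Section 8.3.1.1 also divides SAE reporting at the end of the active collection period, which suggests that time since the last dose governs, not study exit.

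That reading is reasonable, but the text does not settle it. The 28-day rule carries its own proviso for exceptions stated below, and the release from active seeking comes later in the same section and turns on the end of study participation, which 7.2 places at ET. Even if the exception is read broadly, the AE gap becomes permitted but is not closed, and the pregnancy rule in 8.3.5.1 has no such exception.

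Other safeguards exist, but none is a planned inquiry at 28 days:
- Unplanned visits (SoA) are at the investigator's discretion.
- The duty in 8.3.3 to "proactively follow each participant at subsequent visits/contacts" concerns events already reported.
- Under 5.3.4 the participant is told to "call immediately if the selected contraception method is discontinued or if pregnancy is known or suspected", which relies on the participant.
- SAEs learned of later remain reportable (8.3.1, 8.3.1.1), and Appendix 4 covers pregnancies found after IP has stopped; both are passive.
- The Withdrawal of Consent text protects those who ask only to stop treatment, and 7.3 covers missed visits. Neither covers a formal exit from the study.

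What stands of the objection: the affected group is narrow and of unknown size, the shortfall counts scheduled days and not missed events, and the V11 point is small.

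**Conclusion.** The concern holds. For a participant who leaves the study 0 to 27 days after the last dose and still accepts contact, scheduled AE/SAE and pregnancy collection ends 28 to 1 days before the protocol's own minimum. After a formal exit at V10 the shortfall is 11 to 24 days, if the last dose was on the day of V9. Participants who only stop IP are generally unaffected, and those who withdraw consent to contact are rightly excluded.

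The absence of a scheduled contact is certain. How many participants it touches, and how many events would be missed, is unknown. It should be corrected because the window is a safety minimum the protocol sets for itself and the remedy is small.

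**What to change.** 1. In 7.2 and the SoA, add one phone contact 28 to 35 days after the last dose for participants whose ET visit or study exit is fewer than 28 days after that dose and who have not withdrawn consent to contact. It should cover AEs/SAEs, concomitant medication, and contraception and pregnancy. Participation still ends as 7.2 says, and the participant may decline. The call falls 28 − g to 35 − g days after exit: 28 to 35 days if g = 0, 1 to 8 days if g = 27, so always after ET.
2. In 8.3.1, state that the release from active seeking after study participation does not shorten the 28-day minimum.
3. Optional: keep V11 at Days 140-147 and add that it must be at least 28 days after the last dose. The possible interval changes from 25-38 days (140 − 115 to 147 − 109) to 28-38 days, and no V11 window moves earlier.

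The cost is one call per reachable early leaver and a few wording edits, with no added clinic visit or sample. Some leavers will decline, so collection will still be incomplete.
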